8.2.6 Concordance correlation coefficient

The concordance correlation coefficient is a popular indices for assessing the agreement between quantitative measurements taken from different observers (methods). Chia-Cheng Chen et, al. described a repeated measurements method of the concordance correlation coefficient to test the agreement between two measurements (doi:10.1016/j.csda.2012.11.004). To consider that there are N randomly selected subjects where measurements are taken by j observers (fixed) at k time points (random)

Computes Concordance Correlation Coefficient through R language. The epi.ccc of CRAN (Comprehensive R Archive Network) well described the usage and arguments. The formula being used is "epi.ccc(x, y, ci = "asymptotic", conf.level = 0.95, rep.measure = TRUE, subjectid) ", while "x" and "y" representing the sets of two measurements, "ci" indicating the method to be used (z-transform/asymptotic), "conf.level" must be a single number from 0-1, "rep.measure" indicating whether the observations are repeated or not in a logical value (TRUE/FALSE), and "subjectid" is a factor providing details of the observer identifier if rep.measure == TRUE.

Both x and y values need to be present for a measurement pair to be included in the

analysis. If either or both values are missing (i.e. coded NA) then the measurement pair is deleted before analysis.

8.2.7 The outlier of RR estimation

We will use the Tukey approach to identify the outliers of RR estimation, while the difference of AirRR, and ManCRR estimation reach the outside of the interval (Q1-1.5*IQR, Q3+1.5*IQR) will be identified as outliers. The number of outliers in the ITT dataset will be counted and plotted in a box chart on the final report.

8.3 **Protocol Deviations**

A protocol deviation could take place in circumstances where devices malfunction, calibrations, or interrupting the recording by emergency issues. As aforementioned, missing data of a certain period could be introduced into the final result. The missing data episodes will be reported to the DSMB and eliminated from the final statistical result.

8.4 Demographic and Baseline Variables

Subjects will be demonstrated as the number of patients with percentage in the group. Gender will be recorded into male and female and demonstrated as the number of patients with percentage in the group. Age will be recorded into 5 groups (22-34,35-44,45-54,55-64,65 plus) and demonstrated as the number of patients with percentage in the group. Height, weight, BMI and neck circumference will be recorded, the mean value and standard deviation of them will be calculated and demonstrated. Type of procedures will be recorded, each of the group will be demonstrated as the number of patients with percentage in the group. Duration during procedure and PACU will be recorded, the mean value and standard deviation of them will be calculated and demonstrated. Charles Comorbidity score will be recorded into 16 groups (myocardial infarction, congestive heart failure, peripheral vascular disease, cerebrovascular disease, dementia, chronic pulmonary disease, connective tissue disease, ulcer disease, stroke or transient ischemic stroke, diabetes, hemiplegia, moderate to severe renal disease, diabetes with end organ damage, any tumor, leukemia, lymphoma) and demonstrated as the number of patients with percentage in the group.

8.5 Concurrent Illnesses and Medical Conditions

We will employ the Charlson comorbidity scale and also record the major operation/examination of patients who were enrolled in this study to indicate the concurrent illnesses and medical conditions. Furthermore, the pre-anesthesia evaluation result, including the ASA score, will be also recorded and reported to reveal the patient risk landscape of our study.

The Charlson comorbidity scale records the following disease as reference:

| 1. Myocardial infarct |
|--------------------------------|
| 2. Congestive heart failure |
| 3. Peripheral vascular disease |
| 4. Cerebrovascular disease |

Evaluating the Non-Inferiority of Airmod to Capnostream™35 on Respiratory Rate Monitoring and User Experience Clinical Evaluation

| 5. Dementia |
|--|
| 6. Chronic pulmonary disease |
| 7. Connective tissue disease |
| 8. Ulcer disease |
| 9. Stroke or transient ischemic stroke |
| 10. Diabetes |
| 11. Hemiplegia |
| 12. Moderate to severe renal disease |
| 13. Diabetes with end organ damage |
| 14. Any tumor |
| 15. Leukemia |
| 16. Lymphoma |
| 17. Moderate or severe liver disease |
| 18. Metastatic solid tumor |
| 19. AIDS |

Table 4. Diseases recorded in Charlson comorbidity

We will further record and analyze the patient demographic with ICD-10 PCS (procedure codes) to indicate the patient population of concurrent illness during the study.

8.6 Treatment Compliance

Not applicable.

9 Efficacy Analyses

To demonstrate the non-inferiority, the Efficacy Analyses included all of the intent to treat population; it followed the objective of study endpoint to measure respiratory rate performance of Airmod (AirRR) in comparison with the reference device (ManCRR and CapRR). The respiratory rate estimation of each device under test (DUT) is described in the unit of the respiratory count per minute from each measurement over time (sampling rate at 1Hz) regardless of actual cause of inhalation event detected by DUT. The efficacy of agreement in the secondary endpoint is evaluated by Bland Altman analysis, a bias between mean and difference, and 99.69% CI at interim analysis and 95.1% at final analysis of the difference between DUTs in an unit difference plot (unit = breaths per minute). Subgroup analysis of each endpoint focuses on various sections and scenarios of anesthesia (from preparation, induction,

interoperation, transportation, and post anesthesia care unit). An obesity group (BMI >=30) is particularly selected to indicate the high risk patients in the procedural sedation and they will be tested as a stratified subgroup in all of the study endpoints.

The primary efficacy analysis of primary endpoints are comparing the difference of AirRR and ManCRR to reject the null hypothesis (difference of estimation is greater than the non-inferiority limit : -3) under 95% level of confidence interval of all ITT population. The $\mu\alpha$ denotes the respiratory counts of AirRR per minute, and the $\mu\beta$ denotes the respiratory counts of ManCRR per minute. The respiratory count per minute is the mean of recorded samples (eliminating the missing or non-detecting data

point) in each minute. Respiratory counts per minute represent the respiratory rate and are tested in the primary objective hypothesis with the type I error of 0.025, and Type 2 error of 0.2, and the power is 0.8 with single tail non-inferiority analysis.

| Step | Summary |
|-------------------------------|---|
| Objective | Non-inferiority: H0:μα-μβ> d _{NI} vs H1:μα-μβ≤ d _{NI} |
| Endpoint | Margin_1 >-3; Margin_2 >-2 |
| Error | Type I error α=0.025 (one-sided) |
| | Type II errorβ=0.2, Power 1-β=0.8 |
| Non-inferiority limit | d _N = -3 Brpm |
| Population standard deviation | σ=3.29647 |
| Others | r=1, dropout rate=0.3% |

Reference from our pilot study in 25 cases

Table 6. Statistical information referencing from pilot study

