9 STATISTICAL CONSIDERATIONS

9.1 STATISTICAL HYPOTHESES

Primary Analysis:

In this study, all the measurements were conducted in the same subject, and the clocking variance would be limited by investigator justification procedure to acquire the utmost matching recording. The study design is a paired non-inferiority test to evaluate accuracy and performance of respiratory rate (RR) measurement from Airmod compared to Capnostream™35. The primary objective is to establish the non-inferiority. The primary end goal is to test the entire effect at the margin of 3 breaths per minute (bpm). The non-inferiority is a directional (one-sided) test. The null hypothesis (H_0) and alternative (H_1) are defined as:

$$H_0: \mu_{\text{AirRR}} - \mu_{\text{ManCRR}} < -3; \\ H_1: \mu_{\text{AirRR}} - \mu_{\text{ManCRR}} \geq -3.$$

Details refer to the SAP.

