9.4.2 ANALYSIS OF THE PRIMARY EFFICACY ENDPOINT(S)

In this study, all the measurements were conducted in the same subject, and the clocking variance would be limited by investigator justification procedure to acquire the utmost matching recording. The study design is a paired non-inferiority test to evaluate accuracy and performance of respiratory rate (RR) measurement from Airmod compared to Capnostream™35. The primary objective is to establish the non-inferiority. The primary end goal is to test the entire effect at the margin of 3 breaths per minute (bpm). The non-inferiority is a directional (one-sided) test. The null hypothesis (H0) and alternative (H1) are defined as:

$$\begin{aligned} H_0: \mu_{\text{AirRR}} - \mu_{\text{ManCRR}} &< -3; \\ H_1: \mu_{\text{AirRR}} - \mu_{\text{ManCRR}} &\geq -3. \end{aligned}$$

At the interim analysis, under 99.69% CI, when reject the null hypothesis (H0) indicates the non-inferiority.

At the final analysis, under 95.1% CI, when reject the null hypothesis (H0) indicates the non-inferiority.

A subgroup analysis for those subjects with $\text{BMI} \geq 30$ will follow the original study design in a stratified sample pool to test the non-inferiority at the margin of 3 bpm.

According to 7.2, part of the measurement result within subject will be censored and excluded in the paired non-inferiority test. The principle of exclusion is based on the investigator reported failure event/period of Airmod or Capnostream™35, the report will be confirmed by the principal investigator. The data prior to discontinuation or following a fixed machine failure period will be included in the paired non-inferiority test.

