4.4 Endpoints

Primary Endpoint:

The difference between AirRR and ManCRR, which is greater than -3 establishes non-inferiority. The unit in this calculation is bpm and sampling rate is 1 Hz.

Secondary Endpoints:

1. The accuracy of inhalation classification in the segmentation basis is greater than 82.5% at the 95% Cl. The performance metrics (F1-socre, MAPE) at event level will be demonstrated and target for F1-score > 0.8, MAPE < 0.5.

2. To measure the agreement of AirRR and ManCRR on concordance correlation coefficient, and on their mean and bias by Bland-Altman analysis.

3. Use paired t-test to compare the response time of Airmod versus Capnography on Capnostream[™]35 after administration of jaw thrust. In the target of p<0.05 indicates significance.

4.1. The difference of ManCRR minus AirRR and ManCRR minus CapRR indicates non-inferiority at margin of 3 bpm (M1) and sampling rate 1Hz.

4.2. The difference of ManCRR minus AirRR and ManCRR minus CapRR indicates non-inferiority at margin of 2 bpm (M2) and sampling rate 1Hz.

5. The absence of unanticipated serious adverse device effect (USADE) during study period and the questionnaire.

Evaluating the Non-Inferiority of Airmod to Capnostream™35 on Respiratory Rate Monitoring and User Experience Clinical Evaluation

[Time Frame:

Non-Anesthesia Stage: Up to 40 patients will be randomly assigned to non-anesthesia stage assessment, the measurement will be evaluated after enrollment with ICF, at the non-operating room (NOR) area. (5~30 minutes)

Procedure Stage: From firstly anesthetic administration to end of procedure. (Depends on procedure 10mins ~ few hours)

Transportation Stage: During transportation of subjects. (1~10 minutes)

Post anesthesia care unit stage : From subjects arrive post anesthesia care unit (PACU) to discharge from PACU (PAR or PADSS score \geq 9) (At least 15 minutes)]

5 Study Methods

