7.5.5 Adjustment of p-value

On the confidence interval analysis in this study, we adopt OBrien-Fleming to determine the nominal significance level α =0.00153 at the interim analysis for the 150 samples. Furthermore, at the end of the study the O'Brien-Fleming determines the nominal significance level at 0.02450 to establish the target of our study confidence interval.

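### SAP 9.1 states the primary null and alternative hypotheses the wrong way round, and the test in its intended direction places no upper limit on over-reading

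*SAP*

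**What the plan says.** The difference tested is AirRR minus ManCRR, with a limit of -3 bpm.

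- **SAP 9.1, text:** the analysis is to "reject the null hypothesis (difference of estimation is greater than the non-inferiority limit : -3) under 95% level of confidence interval".
- **SAP Table 6, Objective row:** the hypotheses open "Non-inferiority: H0:μα-μβ> d", where d is the limit of -3; H1 is the complement, at or below the limit.
- **SAP Table 6, Endpoint row:** "Margin_1 >-3; Margin_2 >-2", the opposite direction in the same table.
- **SAP 4.4:** "The difference between AirRR and ManCRR, which is greater than -3 establishes non-inferiority".
- **Protocol 9.1 and 9.4.2:** H0 is a difference below -3 and H1 a difference of -3 or more. Protocol 9.4.2 adds: "The non-inferiority is a directional (one-sided) test".
- **Confidence level:** SAP 9.1 gives 95%. Protocol 9.4.2 and the opening of SAP 9 give 99.69% at the interim and 95.1% at the final analysis ("At the final analysis, under 95.1% CI, when reject the null hypothesis (H0) indicates the non-inferiority"). SAP 7.5.5 agrees with the latter: O'Brien-Fleming "determines the nominal significance level at 0.02450 to establish the target of our study confidence interval".

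The primary objective in both documents concerns the accuracy and performance of the respiratory rate measurement.

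**The concern.** There are two separate problems and one small one.

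1. **Reversed hypotheses.** The protocol leaves the details to the SAP, and the SAP section that defines the primary test has the decision rule backwards. A programmer following Table 6 would declare success when the device under-reads by more than 3 bpm.

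2. **No upper limit.** Put the right way round, the test rules out only under-reading. A rate reading has no better direction: reading high is as much an error as reading low. Protocol 2.2 names respiratory depression as a common adverse effect of sedation, and over-reading is the error that would hide a falling rate. A positive primary result would not by itself support the accuracy objective.

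3. **Confidence level.** The 95% in SAP 9.1 does not match the group-sequential levels given elsewhere.

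**Working it through.** **Inputs.** SD 3.29647 (SAP Table 6, pilot of 25 cases). Boundaries z = 2.9626 at the interim and 1.9686 at the final analysis (SAP 9.1.1). N = 150 at the interim. Final N = 180 (300 less the protocol's 40% dropout: 300 × 0.6) or 300 (the SAP's 0.3% dropout leaves about 299). *Assumptions:* one mean difference per subject, and 3.29647 is the SD of those paired differences; the SAP calls it only a population SD.

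**The plan's own figures reproduce.** 1 - Φ(2.9626) = 0.00153 and 1 - Φ(1.9686) = 0.02450. The matching intervals are 1 - 2 × 0.00153 = 99.69% and 1 - 2 × 0.0245 = 95.1%. With correlation √0.5 between looks, overall one-sided alpha is 0.0250. Using 1.95996 (a 95% interval) at the final look gives 0.0255.

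**Formulas.** SE = 3.29647/√N, which is 0.269 (N = 150), 0.246 (180) and 0.190 (300). For true bias b:

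- SAP 9.1 read literally: Φ((-3 - b)/SE - z)
- Protocol direction, lower limit only: Φ((3 + b)/SE - z)
- Whole interval within (-3, +3): Φ((3 - b)/SE - z) - Φ((-3 - b)/SE + z)

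**SAP 9.1 read literally, N = 180.** An unbiased device succeeds with probability below 0.0001. One under-reading by 5 bpm succeeds with probability above 0.9999.

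**Protocol direction against an added +3 limit:**

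| True bias (bpm) | Lower limit only, all three N | Within ±3, interim N = 150 | Within ±3, N = 180 | Within ±3, N = 300 |
|---|---|---|---|---|
| 0 | >0.9999 | >0.9999 | >0.9999 | >0.9999 |
| +2 | >0.9999 | 0.77 | 0.982 | 0.9995 |
| +2.5 | >0.9999 | 0.13 | 0.53 | 0.74 |
| +3 | >0.9999 | 0.0015 | 0.0245 | 0.0245 |
| +5, +10 | >0.9999 | <0.0001 | <0.0001 | <0.0001 |

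Worked case, b = +2.5, N = 180: (3 - 2.5)/0.2457 - 1.9686 = 0.066 and Φ(0.066) = 0.53; the second term is negligible.

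**SD sensitivity.** If 3.29647 is a per-method SD, the paired SD is √(2(1 - ρ)) × 3.29647: 4.66 at ρ = 0 and 1.47 at ρ = 0.9. At N = 180, power of the ±3 rule at +2.5 then runs from 0.30 to 0.995. Power at zero bias, and the lower-limit-only pass probability at +3 to +10, stay above 0.9999.

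**Does anything else cap over-reading?**

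- The SAP amendment table drops readings outside 4 to 35 breaths per minute. That is a data exclusion: a true 10 read as 20 stays in.
- The 82.5% accuracy, F1 and MAPE targets (SAP 9.2.1) cover only the less sensitive periods and compare with ManARR. If F1 is scored by event, as 9.2.1 says, 0.8 with recall 1 needs precision 1/(2/0.8 - 1) = 0.667. That tolerates just under 1.5 detections per true breath.
- Bland-Altman (protocol 9.4.3) compares the data with their own limits of agreement. Concordance and percent deviation have no threshold.
- Secondary endpoints 4.1 and 4.2 use ManCRR minus AirRR without a stated direction. A rule of above -3 would cap over-reading at +3; a rule of below +3 would only repeat the primary bound. Either way they do not gate the primary claim.

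**The case against.** The strongest reply has four parts.

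- **The reversal is a slip.** The Endpoint row of Table 6, SAP 4.4 and the protocol all agree on direction, and nobody would knowingly apply the literal rule. That is true, and the error is one of drafting; it still stands in the primary hypothesis, in both sentence and table.
- **One-sidedness was declared.** The protocol chooses a directional test of being no worse than the comparator, and an upper limit turns it into an equivalence test. This is fair as a description. It does not answer why an accuracy objective should tolerate unlimited error on one side.
- **Part of SAP 9.1 is not visible.** The opening of that section was not in the copy reviewed, so an upper limit there cannot be strictly excluded. SAP 4.4 and protocol 9.1 and 9.4.2 state the endpoint without one.
- **The figures depend on the unit of analysis, and the fix has a subgroup cost.** SAP 9.1 speaks of per-minute counts, and 9.1.1 of both minute and subject bases. A smaller standard error would only raise the chance that an over-reading device passes. The BMI ≥ 30 subgroup follows the same design: with 30 subjects and a final z of 1.9686, the ±3 rule has power 0.997 at zero bias but 0.38 at +2.

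Over-reading would also be visible in the reported intervals and plots. Visible is not the same as gating.

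**Conclusion.** The concern holds, and both main parts must be fixed before analysis. SAP 9.1 and the Objective row of Table 6 contradict SAP 4.4, the same table's Endpoint row and the protocol. In the intended direction, no visible text stops a device that over-reads by 3 to 10 bpm from being declared non-inferior, and it would be so declared with probability above 0.9999. That result does not depend on whether the paired SD is 1.47 or 4.66. It does rest on one value per subject and a normal approximation. The +3 upper limit is an assumption borrowed from the plan's own margin. The confidence-level mismatch is minor: 0.0255 against 0.0250.

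**What to change.** 1. In the SAP 9.1 text and Table 6, restate the hypotheses as H0: AirRR - ManCRR ≤ -3 against H1: > -3. Align the equality sign in protocol 9.1 and 9.4.2, which currently place exactly -3 in H1.
2. In the primary endpoint and hypotheses (SAP 4.4, 9.1, Table 6; protocol synopsis, sections 3, 9.1 and 9.4.2), require the whole interval for AirRR - ManCRR to lie within (-3, +3). If the sponsor prefers another upper limit, state and justify it.
3. State the direction of secondary endpoints 4.1 and 4.2.
4. In SAP 9.1, replace the 95% level with 99.69% at the interim and 95.1% at the final analysis, keeping 0.025 as the overall one-sided type I error.

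**Cost.** Wording changes in both documents, with IRB review of the protocol amendment. No extra patients are needed, because the planned two-sided intervals already supply an upper bound. The price is that an over-reading device would now fail, and power falls as true over-reading nears +3. At +2.5 with N = 180 it is 0.53, or 0.30 to 0.995 across the SD range above.

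### SAP 9.1 puts the primary non-inferiority test on a 95% confidence interval, while Protocol 9.4.2 and the SAP's own alpha plan call for 99.69% at the interim and 95.1% at the final

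*SAP*

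**What the plan says.** **The sentence at issue.** SAP 9.1 describes the primary comparison of AirRR with ManCRR as a rejection of the null hypothesis "under 95% level of confidence interval of all ITT population". It adds that the per-minute rates "are tested in the primary objective hypothesis with the type I error of 0.025", with type II error 0.2 and power 0.8. The available text of 9.1 does not link the 95% to either look.

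**The levels given elsewhere for the same decision.**

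- Protocol 9.4.2 (primary endpoint): "The non-inferiority is a directional (one-sided) test". The interim uses a 99.69% interval. For the end of the study: "At the final analysis, under 95.1% CI, when reject the null hypothesis (H0) indicates the non-inferiority".
- Protocol 9.4.6 and SAP 7.1: nominal levels 0.00153 at 150 subjects and 0.02450 at 300 subjects.
- SAP 7.5.5: the final O'Brien-Fleming step "determines the nominal significance level at 0.02450 to establish the target of our study confidence interval".
- SAP 9.1.1, boundary table: information 50% and 100%, one-sided levels 0.00153 and 0.02450, z boundaries 2.9626 and 1.9686.
- SAP section 9, opening paragraph: 99.69% and 95.1% again, but in the sentence on the agreement endpoint.

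**The role of the interim.** Under Protocol 9.4.2, rejecting the null at the interim shows non-inferiority. SAP 7.5.1 says the interim can establish early success. SAP 7.5.3 says no efficacy stopping rule is applied, and concludes that an interim failure does not halt the study.

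**The concern.** The pass/fail rule for the primary endpoint of a pivotal study should have one value, fixed before the data are seen. Here the section that defines the primary analysis names the interval that would apply with a single look, while the rest of the plan names the interval adjusted for two looks. The protocol refers the reader to the SAP for statistical detail, so an analyst could reasonably programme the final test from SAP 9.1. In the SAP text available, 95% is the only interval level attached by name to the primary test.

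Two things are at stake. A lower limit could clear -3 under one level and miss it under the other. And the overall error could rise above 0.025 if the unadjusted interval were used after an interim look at which success could be declared.

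**Working it through.** **Inputs.** Overall one-sided alpha 0.025 (SAP 9.1). Looks at information fractions 0.5 and 1, with boundaries 2.9626 and 1.9686 (SAP 9.1.1 table). Final interval 95% (SAP 9.1) or 95.1% (Protocol 9.4.2). Margin -3 bpm. SD 3.29647, from the 25-case pilot (SAP 9.1). The SD is used only in step 4.

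**1. Reproduce the plan's boundaries.** The O'Brien-Fleming-type spending function (Lan-DeMets) at information fraction t = 0.5 gives

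alpha1 = 2[1 - Φ(z(0.9875)/√0.5)] = 0.001525, so z1 = 2.9626.

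The final boundary c solves

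P(Z1 > 2.9626) + P(Z1 ≤ 2.9626, Z2 > c) = 0.025, with corr(Z1, Z2) = √0.5.

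This gives c = 1.9686, a one-sided level of 0.02450. Both looks match the plan. The classic O'Brien-Fleming shape gives 2.797 and 1.977 (0.00258 and 0.02400), which does not match, so the plan used the spending-function form.

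**2. Convert to intervals.** 1 - 2 × 0.00153 = 0.99694, or 99.69%. 1 - 2 × 0.02450 = 0.951, or 95.1%. The protocol's intervals and the SAP's nominal levels are therefore the same rule. A two-sided 95% interval corresponds to z = 1.9600 and one-sided 0.025 at that look alone.

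**3. Overall one-sided type I error**, using the expression in step 1:

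| Interim success claimable? | Final interval | Final z | Overall error |
|---|---|---|---|
| Yes, at 2.9626 | 95.1% | 1.9686 | 0.02500 |
| Yes, at 2.9626 | 95% | 1.9600 | 0.02549 |
| No | 95% | 1.9600 | 0.02500 |

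A simulation of 20 million pairs gave 0.02503 and 0.02552 for the first two rows. The excess in the second row is 0.02549 - 0.02500 = 0.0005.

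Information may not track the subject count exactly, so the fraction was varied from 0.3 to 0.7 (assumption) with the boundaries held fixed:

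| Fraction | Final 95% | Final 95.1% |
|---|---|---|
| 0.3 | 0.0259 | 0.0254 |
| 0.4 | 0.0257 | 0.0252 |
| 0.5 | 0.0255 | 0.0250 |
| 0.6 | 0.0253 | 0.0248 |
| 0.7 | 0.0251 | 0.0247 |

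The difference due to the interval level stays at about 0.0005 throughout.

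**4. Effect on the decision.** Assume 300 independent paired differences with the plan's SD. The standard error is 3.29647/√300 = 0.190 bpm. The half-width is 1.9600 × 0.1903 = 0.3730 bpm at 95% and 1.9686 × 0.1903 = 0.3747 bpm at 95.1%. The gap is 0.0016 bpm. The margin lies 3/0.190, roughly 16 standard errors, from a zero difference.

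**The case against.** The strongest reply is that the plan already fixes the right threshold. The adjusted final level appears in the protocol's own primary-endpoint section, in Protocol 9.4.6, in SAP 7.1 and 7.5.5, and in the SAP 9.1.1 table directly after the sentence at issue. The 0.025 in SAP 9.1 stands beside the type II error, the power and the pilot SD, so it is the overall design alpha, and the two boundaries spend exactly that amount. The 95% may be the same overall alpha written as an interval. Part of SAP 9.1 was not in the text available for this review and might qualify the sentence.

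Much of this stands. A reader might infer that the plan sets a wrong decision threshold, or that its overall type I error exceeds 0.025. The documents support neither as a flat statement. The correct threshold is stated repeatedly in both documents, no figure is miscalculated, and the 0.025 needs no change. An excess over 0.025 requires that 95% actually be used at the final and that success be claimable at the interim. Protocol 9.4.2 and SAP 7.5.1 support the second condition, and SAP 7.5.3 makes it less clear. Nor do the documents support using 95% at both looks, which would give 0.0416: every passage that sets an interim significance level gives 0.00153.

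The reply does not remove the contradiction. SAP 9.1 attaches 95% to the test itself and does not say that it merely expresses the overall alpha. Even on that reading, it is not the interval against which the final result should be judged.

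**Conclusion.** The inconsistency is real and confined to one sentence. The 95% interval in SAP 9.1 conflicts with the 99.69% and 95.1% intervals of Protocol 9.4.2 and with the SAP's own 0.00153 and 0.02450. The overall one-sided alpha of 0.025 is correct as stated.

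The consequence is conditional and very small. It is an overall error of 0.0255 against 0.0250 if 95% is used at the final and interim success may be claimed, taking information fraction 0.5 and jointly normal test statistics. There is no excess if no interim claim is possible. Under the independence assumption in step 4, a lower limit falling between the two intervals is not a realistic outcome. Severity is minor. The reason to act is that a confirmatory decision rule should read the same wherever it appears. The part of SAP 9.1 that was not available should be checked before the text is changed.

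**What to change.** In SAP 9.1, replace the 95% interval with: interim, lower limit of the 99.69% CI above -3 (one-sided 0.00153); final, lower limit of the 95.1% CI above -3 (one-sided 0.02450); overall one-sided alpha 0.025.

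Reconcile SAP 7.5.1 with 7.5.3 by stating whether non-inferiority may be claimed at the interim, and keep Protocol 9.4.2 in line with the answer. That statement settles whether the interim look spends alpha at all.

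The cost is one revised sentence in SAP 9.1 and one clarification in section 7.5, with no change to the sample size. The only downside is a marginally stricter final threshold (z 1.9686 instead of 1.9600), compared with what SAP 9.1 now says.
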